Data Analysis: As in our pilot study, we will define "likely cognitive impairment" as a score ≤ 2 on the MiniCog; while we are aware it is by no means a gold standard, it is based on a well validated cutoff that serves our purpose of identifying patients who may need special approaches during the perioperative period. All analyses will be repeated in the subset of individuals with the greatest degree of cognitive impairment based upon a MiniCog score of (0-1) in order to understand why these individuals were not identified as cognitively impaired. We will first test the sensitivity of standard procedures compared to systematic procedures with MiniCog defined impairment or severe impairment. We will also compare sensitivity and specificity of the standard vs. systematic approach, and vs. the published sensitivity of 75% in comparable populations. As a secondary outcome, we will try to understand the full relationship among our four assessments, for instance whether systematic chart review and patient/informant reports detect individuals not detected by standard MiniCog cutoffs, as such individuals would be important to include as part of a broad "impairment" outcome for Aim 2 and consider in

subsequent work for special care in the perioperative period. Similarly, if we see patients who have received a formal evaluation of cognitive status in a memory clinic, by a primary care physician, or neuropsychological testing, we will try to understand qualitatively how MiniCog scores compare to such evaluations. Another secondary outcome will be how well patient/informant report can augment chart review when the patient does not have a primary care physician within our network. Differences between sensitivities and specificities will be compared using standard methods using confidence intervals.

We will use logistic regression with any delirium as the outcome and cognitive impairment as defined by the MiniCog cutoff (or level of cognitive function as defined by the ordinal MiniCog score, modeled as best fits the data) in univariate analyses and in multivariate models adjusting for demographics (age, gender, education), baseline functional and medical covariates (ASA functional status, METs, frailty). Analogous analyses for our secondary outcomes will use logistic, linear, or Cox proportional hazards models to assess the relationship of MiniCog scores to these outcomes. In univariate analyses, we will compare change in WHODAS in MiniCog-impaired vs. unimpaired patients using Wilcoxon U test and with ordinal MiniCog score using Spearman rank order correlation. Multivariate analyses will model change in WHODAS (ranked or transformed for best model fit) as a function of MiniCog impairment status (or ordinal value as above), controlling for age, gender, education, comorbidity index, and frailty. In exploratory analyses, patients with and without postoperative delirium will be analyzed separately and compared.

Assays performed using blood collected between from the current study will be analyzed in the grant Circulating Extracellular Vesicles as Biomarkers of Postoperative Delirium (grant submission number 1R21 AG061696-01). Co-investigator [name], is the PI of the above grant; no changes to the current protocol will be made for this analysis.

Risks and Discomforts:

Overall, this study poses low risks for the subjects. The sources of risk are of two types in this study, 1) participation in the interviews and cognitive test and 2) the risk of breach of confidential information. The first “risk” of the study is the time necessary to participate in the study assessments. However, in our pilot study, patients viewed the interactions with the research staff as very positive and enjoyable. It is possible that some of the assessments may pose the risk of fatigue or emotional distress. Should a patient become tired or distraught, the interview will be halted. A related “risk” of participation is the potential breach of confidentiality and privacy of the Protected Health

Information. Methods to reduce this risk include all investigators undergoing extensive training in general principles of informed consent, confidentiality, and administering research instruments in a humane, reliable, and valid manner. All data will be deposited into REDCap, a secure, web-based application for research storage and used for research purposes. There will be no interventions as a result of this study. The data gathered will have no effect on the care that the patient is to receive. Both the CPE providers preoperatively evaluating the patient and the surgeon will not have access to the result of the baseline testing.

Potential Benefits:

This study is being performed to advance medical knowledge. There are no expected benefits to individual subjects participating in the study but it will help advance understanding of how preoperative cognitive performance affects perioperative outcomes in older patients. This study has the potential to aid and improve decision-making by physicians and older patients in the future if they reveal a relationship between poor preoperative cognitive status and adverse cognitive and functional postoperative outcomes in older patients.

Monitoring and Quality Assurance:

Regardless of monitoring plans, the principal investigator is ultimately responsible for ensuring that the study is conducted at his/her investigative site in accordance with the IRB-approved protocol and applicable regulations and requirements of the IRB.

The Principal Investigator or a member of the investigative team will monitor each subject at this single site, and will review the accuracy and completeness of all testing, source documents and informed consent.

There will be no Data Safety Monitoring Board as the results of these studies will have no impact on the care that patients receive. The outcomes of the study are intended to be published in a peer-reviewed manuscript to document whether preoperative cognitive screening is a risk factor for adverse postoperative outcomes and the feasibility and cost of preoperative cognitive stratification in the preadmission testing center. All adverse events will be reported to the Partners the Human Research Committee (HRC) in accordance HRC guidelines. A 24-hour/7-day telephone or pager number will be provided for contacting the licensed physician investigator for this purpose.

The research staff will monitor all subjects during the course of study involvement for evidence of any adverse events such as unexpected stress and the testing discontinued and the incident reported to Partners the Human Research Committee within 24 hours of local event awareness (but no later than the next business day). The report will include a complete description of the event, use of all concomitant medications, and the local investigator's assessment of causality of the adverse event. Follow-up evaluations will be done until there is resolution of the adverse events, which are unlikely as this protocol is non-invasive

References:

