
With national geriatric surgery volume large and growing and morbidity high, better understanding of preoperative cognition as a predictor / mediator of outcome has the potential to yield huge clinical and economic dividends. Assuming identification of a problem is the first step in solving it and that cognitive impairment is a form of brain failure, the lack of routine preoperative cognitive screening is presumably a major barrier to improving geriatric surgical care. Having demonstrated already in 289 patients that MiniCog testing is feasible in a preoperative evaluation center and that even non-medical personnel can administer and score it reliably (Preliminary Data), we are optimistic such screening can be implemented broadly. Unclear, however, is whether it is worth doing in terms of providing information about cognitive function that is unavailable from standard sources (patient/informant inquiry, focused chart review) and whether, like dysfunction of other vital organs, preoperative brain dysfunction is relevant to the surgical outcome of seniors.

Because of our success in screening older surgical patient undergoing elective surgical procedures we are now investigating whether the baseline peripheral immune status as measured by inflammatory cytokines in the plasma and white blood cell response to an ex-vivo immune challenge is predicted by the patient's baseline cognitive screening score. This will allow us to determine whether an exaggerated immune response to the surgery is predictive of adverse outcomes in aging patients.

The results of this work will lay the foundation for future studies that treat preoperative cognitive impairment as a risk factor and test interventions to improve geriatric surgical care and outcomes based on it. Examples might include discussion about the appropriateness or timing of surgery, preoperative consultation by a geriatrician, more careful titration of depth of general anesthesia (recently shown to reduce the risk of delirium),^{33,34} or triage to a specialized geriatric care unit postoperatively.^{31,35} Given the prevalence of likely cognitive impairment in our pilot study, preoperative cognitive screening promises to be an excellent low-cost, patient centered, high impact proposition for enhancing surgical outcomes in seniors.

Objectives:

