Our overriding hypothesis is that preoperative cognitive impairment is a risk factor for poor surgical outcomes in seniors and that preoperative screening is superior to standard or systematic clinical processes for identifying at-risk patients.

Objective 1. Assess the marginal benefit of structured preoperative cognitive screening relative to standard or systematic preoperative evaluation for identifying seniors with likely cognitive impairment.

Objective 2. Determine whether preoperative cognitive impairment predicts postoperative outcome.

Objective 3. Determine whether other preoperative variables (mood, social support, history of depression, pain, and health and functional status) predict postoperative outcome.

Subject Selection: This project is designed as a prospective, single-center observational study. The cohort will consist of 500 consenting subjects \geq 70 years of age who present to the BWH Weiner Center for Preoperative Evaluation (CPE) prior to elective thoracic surgery (specifically, thoracoscopic lung resection, lobectomy, thoracotomy, or esophagectomy) or to neurological anterior, posterior cervical, thoraco, or lumbar spine surgery performed by neurosurgeons or orthopedic spine surgeons. 250 subjects undergoing thoracic surgery will be recruited and 500 subjects undergoing spine surgery will be recruited. These ages are chosen as significant clinical data demonstrate increased cognitive impairment in community dwelling elders. Eligibility criteria include: patients \geq 70 years of age with an ASA physical status of I-III presenting for elective thoracic, or orthopedic anterior or posterior cervical, thoraco, or lumbar spine surgery. Exclusion criteria will include history of stroke (not including TIAs) or brain tumor, uncorrected vision or hearing impairment (unable to see pictures or read or hear instructions); limited use of the dominant hand (limited ability to draw); and/or inability to speak, read, or understand English.

An additional cohort of 50 patients aged 45-60 undergoing elective neurological posterior thoracolumbar spine surgery or orthopedic spine surgery with an ASA physical status of I-III will be recruited through the BWH Weiner Center for Preoperative Evaluation (CPE). Eligibility and exclusion criteria will be the same as the aged 70 and older cohort, barring age. The purpose of enrolling this small younger subject population is to compare biomarkers between the two groups.

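### No planned analysis can test whether MiniCog screening is superior to standard or systematic evaluation: the MiniCog is the reference in one analysis and the only cognitive classification in the others

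*Combined protocol and SAP*

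**What the plan says.** The Objectives section states an overriding hypothesis with two parts: that preoperative cognitive impairment is a risk factor for poor surgical outcome, and that "preoperative screening is superior to standard or systematic clinical processes for identifying at-risk patients". Objective 1 is narrower: "Assess the marginal benefit of structured preoperative cognitive screening relative to standard or systematic preoperative evaluation for identifying seniors with likely cognitive impairment". The background section asks "whether it is worth doing in terms of providing information about cognitive function that is unavailable from standard sources".

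The Data Analysis section defines likely cognitive impairment as a MiniCog score of 2 or less, conceding "while we are aware it is by no means a gold standard". The first analysis follows: "We will first test the sensitivity of standard procedures compared to systematic procedures with MiniCog defined impairment or severe impairment". Standard and systematic approaches are then compared with each other and "vs. the published sensitivity of 75% in comparable populations". A secondary analysis asks "whether systematic chart review and patient/informant reports detect individuals not detected by standard MiniCog cutoffs", and says that "such individuals would be important to include as part of a broad" impairment variable for Aim 2. Patients who happen to have had a formal cognitive evaluation are to be compared with their MiniCog scores qualitatively. All analyses are repeated at MiniCog 0–1.

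The outcome models come next. Delirium is regressed on the MiniCog cut-off or ordinal score, with age, gender, education, ASA status, METs and frailty as covariates; Study Procedures adds APOE e4 status. The secondary-outcome and WHODAS models likewise use the MiniCog as the cognitive exposure.

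**The concern.** A superiority claim needs the competing methods to be judged on a yardstick that belongs to none of them. Here the MiniCog is the yardstick in the first set of analyses and the only cognitive classification in the second. The standard-form, record-review and patient/informant classifications, all collected under Study Procedures, enter no specified outcome model.

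The study can therefore report how many MiniCog-positive patients the other sources do not flag. It cannot report whether the MiniCog picks out patients who go on to do badly better than those sources do. A low figure for systematic evaluation would mix true misses with MiniCog false positives in unknown proportion, and could easily be read as support for superiority.

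**Working it through.** The plan gives no power calculation or target figure for this comparison, so there is nothing to reproduce. The check traces the analyses and then illustrates the consequence.

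**1. What each analysis compares**

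| Analysis | Assessed | Against | MiniCog compared with other sources on an independent yardstick? |
|---|---|---|---|
| Sensitivity and specificity | Standard, systematic | MiniCog ≤2 (repeated at 0–1) | No |
| Published 75% | Standard, systematic | External figure; test and reference standard not named | No |
| Relationship among the four assessments | All four | Each other | No; descriptive |
| Formal evaluations | MiniCog | Evaluations some patients happen to have had | Qualitative only |
| Broad impairment variable | Sources pooled | Not taken up in the outcome models | No; pooling is not comparing |
| Delirium, secondary outcomes, WHODAS | MiniCog | Outcome | No; other sources absent |

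If at-risk means likely to have a poor outcome, no comparison is planned. If it means MiniCog-defined impairment, the MiniCog is 100% sensitive and specific by construction and superiority cannot be refuted.

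**2. What an imperfect reference does to the comparator**

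Let q be the MiniCog-positive rate, Se and Sp its true accuracy, and p the true prevalence. For an error-free comparator:

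- apparent sensitivity = Se·p/q = (q − (1−Sp)(1−p))/q
- apparent specificity = Sp(1−p)/(1−q)

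The background section gives pilot values of q: 24% overall and 33% at age ≥75. The pilot enrolled geriatric patients (seniors defined as ≥65) and the main cohort is ≥70, so both are shown. The documents give no MiniCog specificity; Sp of 85/90/95% is assumed throughout.

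(a) Assume Se = 75%, so p = (q − (1−Sp))/(Se − (1−Sp)).

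| q | Implied p | Apparent sensitivity |
|---|---|---|
| 24% | 15 / 21.5 / 27% | 47 / 67 / 85% |
| 33% | 30 / 35 / 40% | 68 / 80 / 91% |

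For example, with q = 0.24 and Sp = 0.90: p = 0.14/0.65 = 0.215, and 0.75 × 0.215/0.24 = 0.67.

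(b) Fix p instead at the ends of the background section's 35–50% prevalence, which includes MCI and depends on definition.

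| q | p | Apparent sensitivity | Apparent specificity | Implied MiniCog Se |
|---|---|---|---|---|
| 24% | 35% | 59 / 73 / 86% | 73 / 77 / 81% | 41 / 50 / 59% |
| 24% | 50% | 69 / 79 / 90% | 56 / 59 / 63% | 33 / 38 / 43% |
| 33% | 35% | 70 / 80 / 90% | 82 / 87 / 92% | 66 / 76 / 85% |
| 33% | 50% | 77 / 85 / 92% | 63 / 67 / 71% | 51 / 56 / 61% |

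Higher prevalence moves the distortion from sensitivity to specificity; it does not remove it.

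(c) An extreme case: true prevalence 24%, systematic evaluation truly 75% sensitive and 95% specific, and a MiniCog no better than chance (24%/76%), with independent errors given true status. Apparent sensitivity is (0.24·0.24·0.75 + 0.76·0.24·0.05)/0.24 = 22%, and apparent specificity is 78%. The worthless test would still be the standard that the better one fails.

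**3. The standard process in the pilot**

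0.24 × 289 ≈ 69 MiniCog-positive patients, of whom the nurse flagged one. Under (a) at q = 24%, about 33 to 59 of the 69 would be true cases, so at most 1/32.5 = 3.1% to 1/58.8 = 1.7% were flagged. MiniCog error alone would not explain that gap. The reference problem therefore bears mainly on systematic evaluation.

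**4. Precision of a direct comparison**

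For a yes/no classifier, AUC = (sensitivity + specificity)/2. With a share d of discordant classifications, no true difference, n1 delirium cases and n0 non-cases, the 95% half-width for the paired AUC difference is 0.5 × 1.96 × √(d/n1 + d/n0). Delirium is taken as 15%, the low end of the background section's 15–80%. Both stated sizes of the older cohort are used.

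| N (n1/n0) | d = 0.2 | 0.3 | 0.4 |
|---|---|---|---|
| 500 (75/425) | 0.055 | 0.067 | 0.078 |
| 750 (112/638) | 0.045 | 0.055 | 0.063 |

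For sensitivity alone, 1.96 × √(d/n1) gives 0.101–0.143 and 0.083–0.117.

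**The case against.** The strongest objection is that the two aims form a chain: Aim 1 asks who is missed without screening, Aim 2 asks whether that status predicts outcome, and at-risk is shorthand for likely impaired. On that reading the plan does what Objective 1 asks. This stands for the marginal-yield question, and standard versus systematic remains valid as relative agreement. It does not rescue superiority, which on that reading holds by definition.

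Second, if the standard process again flags almost nobody, its AUC will be near 0.5 and the univariate delirium model would nearly settle MiniCog versus standard. That is fair, but it depends on the pilot pattern repeating and leaves systematic evaluation untested.

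Third, the repeat at MiniCog 0–1 cannot lower specificity and should normally leave fewer false positives among the positives. True, but the MiniCog is still the reference.

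Fourth, the published 75% may be meant as the MiniCog's own sensitivity, which would make it a benchmark. The documents do not say, and an external figure on an unnamed reference standard is not like for like. The 75% in illustration (a) is likewise only an assumption, which is why (b) drops it.

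Fifth, the accuracy figures quantify reference error rather than the missing test, and 15% delirium is the least favourable end of the range. Both points stand. At 50% delirium with 500 patients the AUC half-width would be 0.039–0.055.

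**Conclusion.** The concern holds. The superiority half of the overriding hypothesis has no analysis that could confirm or refute it. The risk-factor half, and Objective 1 read as marginal yield, are unaffected.

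This conclusion rests on the text of the plan, not on the illustrations. Those show only that the distortion could be large: at the pilot's 24% positive rate, an error-free comparator could appear 47–90% sensitive over the assumed range. The practical gap is greatest for MiniCog versus systematic evaluation. It should be closed before analysis, because a superiority conclusion drawn from the planned table would be unsupported.

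**What to change.** 1. **Test of superiority.** In the same patients (age ≥70, operated on, delirium assessed), compare the standard, systematic and MiniCog ≤2 classifications for predicting postoperative delirium. Use the paired difference in AUC, or in sensitivity and specificity, with confidence intervals, and name the chosen measure in advance. State which combination of record review and patient/informant report counts as systematic-positive. Keep the MiniCog at its fixed cut-off, so that a graded score is not set against yes/no classifications. State that an interval including zero is inconclusive.
2. **Added value, reported separately.** Fit nested logistic models in both directions: MiniCog added to standard plus systematic information, and systematic information added to the MiniCog. Do not call this superiority.
3. **Relabel the existing table** as agreement with the MiniCog, that is, the share of MiniCog-positive patients already flagged. Drop the 75% comparison unless it is tied to the same test and reference standard.

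If the investigators do not want this comparison, the minimum is to reword the hypothesis to match Objective 1.

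The cost is SAP wording and a modest amount of analysis on data already collected under Study Procedures. The drawbacks are a more modest Objective 1 claim and intervals that may not settle small differences. Delirium also tests identification of at-risk patients, not diagnostic accuracy for cognitive impairment.

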depression and pain noted on the patient's preoperative evaluation form will be recorded, as well as past history of delirium or other post-anesthetic complications, use of hearing and/or hearing aids, and medical comorbidites. In addition, patients will be asked if they've had a fall within the last 6 months, whether they've been evaluated for a change in memory or thinking, who accompanied them to their appointment, their employment status and their living situation (alone, institutionalized, living with family members) in a patient survey. The study staff will also administer the MiniCog, a simple cognitive screening tool that takes just 2-4 min to complete and has little or no education, language, or race bias. In addition, the Animal Fluency test will be administered, which is a short cognitive screen that takes one minute to complete. Patients will also complete the self-report cognitive assessment CANTAB Insight Cognitive Exam, using an iPad developed by Cambridge Cognition. This 10 minute assessment measures cognitive health on five axes: executive function, processing speed, attention, working memory, and episodic memory through three cognitive tests: Matching Patterns, Working Memory, and Pairs Associates Learning Tests. Other measures of cognitive impairment will be obtained by study staff through: documentation on the patient's standard preoperative form, patient or informant report of diagnosis or evaluation for cognitive impairment or memory concerns, and systematic medical record review. Each enrolled patient will receive a business card listing the investigators' contact information and be advised to expect a follow up telephone call 6 months and 1 year after surgery to verify data elements and reassess functional outcome.

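### Objective 2 is modelled through the MiniCog alone: a null would not exclude a moderate effect of cognitive impairment, and two other baseline cognitive tests have no planned analysis

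*Combined protocol and SAP*

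**What the plan says.** The Objectives section sets the question as "Determine whether preoperative cognitive impairment predicts postoperative outcome". It names impairment, not a particular test.

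Under Data Analysis, impairment is a MiniCog score of 2 or less. The authors write of this definition, "while we are aware it is by no means a gold standard", and defend it as resting on a validated cutoff that is adequate for their purpose. The models are then:

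- **Delirium:** "We will use logistic regression with any delirium as the outcome and cognitive impairment as defined by the MiniCog cutoff", or alternatively "level of cognitive function as defined by the ordinal MiniCog score, modeled as best fits the data".
- **Secondary outcomes:** logistic, linear or Cox models "to assess the relationship of MiniCog scores to these outcomes".
- **Change in WHODAS:** MiniCog status or ordinal score, both in the univariate tests and in the adjusted model.

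The analyses are also to be repeated for scores of 0-1, which is again the same instrument.

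Study Procedures lists two further baseline tests: "Patients will also complete the self-report cognitive assessment CANTAB Insight Cognitive Exam, using an iPad developed by Cambridge Cognition", a 10-minute test covering five domains, and "In addition, the Animal Fluency test will be administered". Neither is named again, and neither is in Objective 3's list of other predictors.

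Data Analysis does foresee a broad impairment outcome for Aim 2. It would add patients whom chart review or patient/informant report finds and the MiniCog misses. No model uses it.

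**The concern.** A screen that misclassifies some patients mixes impaired and unimpaired people in both of its groups. If the errors are unrelated to outcome, the odds ratio for impairment is pulled toward 1 and power falls. A null MiniCog result could then mean either that impairment has little effect or that the screen blurred it.

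The study will hold other cognitive data that bear on this, but the plan does not say how they will be used. Without prespecification they will either go unused or be tried once the MiniCog result is known, when a positive finding would carry little weight.

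**Working it through.** The plan gives no power, alpha, effect size or sample-size derivation, so there is no figure of its own to reproduce. Everything below is illustrative.

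**1. Which test enters which model**

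| Measure | Collected | In an Objective 2 model |
|---|---|---|
| MiniCog, cutoff or ordinal | Yes | All |
| CANTAB | Yes | None |
| Animal Fluency | Yes | None |
| Broad impairment variable | Components collected | None; not defined |

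Data Analysis refers to four assessments without listing them. The MiniCog plus the preoperative form, patient/informant report and record review makes four, so this does not bring in CANTAB or Animal Fluency.

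**2. Dilution of a true odds ratio of 3.0**

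From the documents: 24% MiniCog-positive in the pilot (age 65 and over). Assumed: sensitivity (se) 0.75-0.85, specificity (sp) 0.85-0.95, and delirium risk 30% in truly impaired and 12.5% in unimpaired patients, so OR = (0.30/0.70)/(0.125/0.875) = 3.0.

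- True prevalence: π = (0.24 − (1 − sp)) / (se − (1 − sp))
- Impaired share of positives: a = π·se/0.24; of negatives: b = π(1 − se)/0.76
- Observed risks: r1 = 0.125 + 0.175a; r0 = 0.125 + 0.175b

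| se / sp | π | a | b | r1 | r0 | Observed OR |
|---|---|---|---|---|---|---|
| 0.75 / 0.85 | 0.150 | 0.469 | 0.049 | 0.207 | 0.134 | 1.69 |
| 0.75 / 0.95 | 0.271 | 0.848 | 0.089 | 0.273 | 0.141 | 2.30 |
| 0.85 / 0.85 | 0.129 | 0.455 | 0.025 | 0.205 | 0.129 | 1.73 |
| 0.85 / 0.95 | 0.238 | 0.841 | 0.047 | 0.272 | 0.133 | 2.43 |

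The range is about 1.7 to 2.4.

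**3. A moderate effect: true odds ratio of 2.0**

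Five assumed settings (π/se/sp): 0.24/0.75/0.90, 0.24/0.75/0.95, 0.35/0.75/0.90, 0.35/0.60/0.95 and 0.50/0.45/0.97. The observed OR is 1.44 to 1.69. Unadjusted power, two-sided 0.05, no dropout, is Φ[(|r1 − r0| − 1.96·SE0)/SE1], with SE0 pooled and SE1 unpooled:

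| N | Delirium | Error-free measure | MiniCog cutoff |
|---|---|---|---|
| 750 | 15% | 87-91% | 38-63% |
| 750 | 25% | 95-98% | 51-76% |
| 500 | 15% | 72-78% | 28-48% |
| 500 | 25% | 85-91% | 37-60% |

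The error-free column is a ceiling, not what the added tests would achieve. For a true OR of 3.0 at N = 750, the cutoff has 68-95% power (15% delirium) or 85-99% (25%).

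**4. What an exact null would exclude**

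Take N = 750, 24% positive and 15% delirium in both groups. The cells are 27, 153, 85.5 and 484.5. SE(log OR) = √(1/27 + 1/153 + 1/85.5 + 1/484.5) = 0.239, so the 95% interval is exp(±1.96 × 0.239) = 0.63 to 1.60. At N = 500 the SE is 0.239 × √1.5 = 0.293 and the upper limit is 1.78. Most of the 1.44-1.69 range from step 3 lies inside the first interval and all of it inside the second.

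**5. Whether a composite would do better**

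The mean of three standardised scores with correlations c1, c2, c3 to true cognition has correlation (c1 + c2 + c3)/√(3 + 2Σr), where Σr sums the three pairwise correlations.

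- MiniCog 0.7, CANTAB 0.7, fluency 0.6, independent errors: Σr = 0.49 + 0.42 + 0.42 = 1.33, giving 2.0/√5.66 = 0.84, above 0.7.
- MiniCog 0.7, CANTAB 0.5, fluency 0.4, error correlation 0.5: each pair adds 0.5√((1 − ci²)(1 − cj²)), so Σr = 0.659 + 0.607 + 0.597 = 1.863, giving 1.6/√6.727 = 0.62, below 0.7.

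All these correlations are assumptions. The gain can be positive or negative.

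**The case against.** The strongest reply is that the MiniCog result is itself the exposure of interest. The overriding hypothesis concerns preoperative screening, the background stresses screening by regular clinic staff, and Monitoring and Quality Assurance says publication will report whether preoperative screening is a risk factor. For that question there is no dilution. With 24% positive, the OR detectable with 80% power is 1.70-1.88 at N = 750 and 1.91-2.14 at N = 500. This stands, and it is why the MiniCog should remain primary.

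A reader might infer that a null MiniCog result cannot be interpreted at all. The documents do not support that: it would have a readable confidence interval for the screening association, and at N = 750 a true OR near 3 would usually be detected.

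A reader might also infer that the association is certainly diluted. That needs errors unrelated to outcome. Risks and Discomforts says that the clinic providers and the surgeon do not see the baseline results, but it says nothing of the delirium assessors, so bias in the other direction cannot be excluded.

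Finally, the plan does recognise a broader definition for Aim 2. That is fair credit, but the definition stays unspecified and omits both added tests.

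**Conclusion.** The point holds in a limited form. Objective 2 asks about impairment, every model uses one admittedly imperfect screen, and two cognitive tests already collected have no stated role. A null would leave a moderate effect of impairment open, though it would still inform the screening question.

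The size is illustrative. It rests on assumed specificity, on an assumed sensitivity range, on non-differential error, and on a pilot rate from patients aged 65 and over applied to a cohort aged 70 and over. The plan's 75% published sensitivity is not tied to a named instrument. With 24% positive, 75% sensitivity requires true prevalence of at most 0.24/0.75 = 32%, below the 35-50% quoted in the background, although those figures come from different populations.

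No power gain from adding CANTAB and Animal Fluency can be claimed. The case for using them is that they are already being collected and that a prespecified analysis is more credible than a later one. This is a cheap improvement, not a fatal flaw.

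**What to change.** 1. Keep the MiniCog model as primary for Objective 2, and interpret a null by its confidence interval.
2. Add to Data Analysis one declared-secondary exposure for the delirium and WHODAS models, with the same covariates: the mean of the standardised MiniCog, CANTAB and Animal Fluency scores, with at least two of the three present. Name the CANTAB summary score and align the direction of all three. Report the estimate and interval beside the ordinal MiniCog result.
3. Define the broad Aim 2 impairment variable and use it in a sensitivity analysis.
4. Reconcile the cohort of 500 in the opening of Subject Selection with the 750 stated later in that section.

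Two additions should be avoided. Calling Objective 2 negative only if both exposures are null would give two uncontrolled chances of a positive. Reading a positive composite beside a null MiniCog as a failure of the screen would confuse cognitive level, including variation in the normal range, with screening error.

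The cost is one paragraph, one extra model per main outcome and one sensitivity analysis, with no new data. The downside is one more secondary test per main outcome, using a composite that measures cognitive level and is not a clinic tool.
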